5.5.3 Secondary Efficacy Endpoints

5.5.3.1 Key Secondary Efficacy Endpoints

5.5.3.1.1 1st Key Secondary Endpoint: TSC-associated Seizure Treatment

Responders (≥50% Reduction in TSC-associated Seizure Frequency)

Blinded Phase:

The proportion of patients considered treatment responders, defined as those with a ≥50% reduction in TSC-associated seizure frequency from baseline during the treatment period, for patients who have not withdrawn from the trial during the treatment period, will be summarized by treatment arm and analyzed using a Cochran–Mantel–Haenszel (CMH) test stratified by age group.

The proportion of patients who are considered treatment responders, the difference in proportions along with the 95% CI for the difference, the estimated odds ratios (GWP42003-P arms vs. placebo), 95% CI for the odds ratios, and the p-values from the CMH test will be presented. If no patients in a particular treatment arm are considered responders then the odds ratio and 95% CI for the odds ratio will not be calculated.

The analysis will be performed on the ITT analysis set and repeated on the PP analysis set.

Sensitivity analyses will be performed on the ITT analysis set, repeating the above analysis, using data for the maintenance period only, the titration period and during each 4 weeks of the maintenance period (Week 1 to 4, Week 5 to 8 and Week 9 to 12 of the 12 week maintenance period).

Analyses on the maintenance period, titration period and by each 4 weeks of the maintenance period will include only patients who have at least 7 days of seizure data within each period.

Open-label Extension:

Descriptive summaries described above for the blinded phase will be repeated for OLE periods. However, for the OLE periods, withdrawn patients may be considered responders.

5.5.3.1.2 2nd Key Secondary Endpoint: Subject/Caregiver Global Impression of Change

Blinded Phase:

The SGIC and CGIC comprise the following questions to be rated on a 7-point scale:

CGIC:

- Since your child started treatment, please assess the status of your child's overall condition (comparing their condition now to their condition before treatment) using the scale below.

SGIC:

- Since you started treatment, please assess the status of your overall condition (comparing your condition now to your condition before treatment) using the scale below.

The possible responses are: Very Much Improved; Much Improved; Slightly Improved; No Change; Slightly Worse; Much Worse; Very Much Worse.

The responses above are based on comparison with a brief description of the patient's overall condition used as a memory aid from Visit 3.

Each response will be coded with a score from 1 to 7, where 1 = Very Much Improved, and 7 = Very Much Worse.

The SGIC and CGIC response/score, recorded at each visit, will be summarized separately, on both a categorical and continuous scale, by treatment arm.

It is anticipated that only a small percentage of patients will complete the subject version of the questionnaire. Hence, no analyses will be performed for the SGIC.

A combined score will be used as the primary analysis for this endpoint. The combined score will be defined as follows:

- If both a CGIC and SGIC are completed then the CGIC will be used.
- If only a CGIC is completed then the CGIC will be used.
- If only a SGIC is completed then the SGIC will be used.

The score at the end of treatment visit and last visit (if different to the end of treatment) will be analyzed using ordinal logistic regression. Proportional odds modelling will be carried out by including treatment arm as a factor. The estimated odds ratio (GWP42003-P vs. placebo), 95% CI for the odds ratio, and the p-value testing the null hypothesis that the odds ratio is equal to 1, will be presented. Analysis performed at the last visit will be considered the primary analysis for this endpoint, with the analysis at the end of treatment visit considered a sensitivity analysis.

Should the proportional odds assumption not hold, i.e. if the p-value for the score test for proportional odds assumption is <0.05 , then, as a sensitivity analysis, the scores will also be analyzed using a Cochran-Armitage trend test. This will be presented together with the results of the ordinal logistic regression.

Since this analysis uses a combination of caregiver and subject ratings, a sensitivity analysis will be performed using only the CGIC score and using the same analyses as above.

The analysis will be performed on the ITT analysis set and repeated on the PP analysis set.

Open-label Extension:

Descriptive summaries described above for the blinded phase will be repeated for OLE visits.

5.5.3.1.3 3rd Key Secondary Endpoint: Total Seizures

Blinded Phase:

Summaries and analyses of total seizures (see Section 5.1.3.9) will be performed as per the primary endpoint (Section 5.5.2).

The analysis will be performed on the ITT analysis set and repeated on the PP analysis set.

Sensitivity analyses will be performed on the ITT analysis set, repeating the above analysis, using data for only the maintenance period, titration period, and during each 4 weeks of the maintenance period (Week 1 to 4, Week 5 to 8 and Week 9 to 12 of the 12 week maintenance period).

Analyses on the maintenance period, titration period and by each 4 weeks of the maintenance period will include only patients who have at least 7 days of seizure data within each period.

Open-label Extension:

Summaries will be performed for the OLE periods as described in the OLE portion of the primary endpoint section (Section 5.5.2).

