5.1.3.6 Maintenance Period

The maintenance period of the double-blind phase is defined as Day 29 to Day 113.

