2.3.3 Robustness to Withdrawn Patients

There were higher proportions of patients in each treatment arm that withdrew during the blinded phase treatment period when compared with placebo. In order to assess the robustness of the results, 2 analyses in the following sections are proposed.

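### The 7-day data rule drops early withdrawers from the period-specific responder analyses, although the parent analysis counts them as non-responders, so those differences can be biased towards active.

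*SAP*

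**What the plan says.** SAP 5.5.3.1.1 defines the first key secondary endpoint as a reduction of at least 50% in TSC-associated seizure frequency, "for patients who have not withdrawn from the trial during the treatment period, will be summarized by treatment arm". On the analysis set it says: "The analysis will be performed on the ITT analysis set and repeated on the PP analysis set". SAP 5.2.2 defines the ITT set as all randomized patients who took at least one dose. For the open-label extension the same section reverses the rule on withdrawal: "However, for the OLE periods, withdrawn patients may be considered responders".

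The period-specific versions are introduced as repeats: "Sensitivity analyses will be performed on the ITT analysis set, repeating the above analysis, using data for the maintenance period only, the titration period", followed by each 4-week block of maintenance. The next paragraph says that these analyses "will include only patients who have at least 7 days of seizure data within each period". SAP 5.5.3.2.1 has the same restriction for the ≥25% and ≥75% responders and for seizure freedom.

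SAP 5.1.3.6 fixes the period: "The maintenance period of the double-blind phase is defined as Day 29 to Day 113". Addendum 2.3.3 reports on withdrawal: "There were higher proportions of patients in each treatment arm that withdrew during the blinded phase treatment period when compared with placebo". It gives no counts and no timing.

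**The concern.** The parent analysis already classifies a withdrawn patient as a non-responder, so no seizure rate is needed for that patient. A minimum number of days makes sense for a rate that would otherwise rest on a handful of days. Applied to a responder proportion, it takes out of the denominator patients whose outcome is already settled.

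The removal depends on withdrawal, which happens after randomization and was more common on active. What is labelled an ITT repeat becomes, in part, a comparison among patients who stayed long enough. A sensitivity analysis of the first key secondary endpoint could then look better than its parent only because the denominator changed.

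**Working it through.** **Plan's own figures.** The SAP states no number for the responder analyses. The 70 per arm comes from SAP 3.2 (210 patients, 2:2:1:1, placebo pooled). It is consistent with the stated 90% power: a difference of 35 points with SD 60 needs 62 per arm for a comparison of means, 65 after dividing by a Wilcoxon efficiency of 3/π, and 72 with the conservative efficiency of 0.864.

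**Who is dropped.** Maintenance has 113 − 29 + 1 = 85 days, and its seventh day is Day 29 + 6 = 35. With daily reporting, the whole-maintenance analysis drops patients whose data end before Day 35. If the 4-week blocks start on Days 29, 57 and 85, the cut-offs are Days 35, 63 and 91, so more withdrawals fall before the cut-off in each later block.

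**Formula.** Let p be the responder proportion among patients kept by the rule and w the share of the arm dropped.

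- 7-day rule: difference = p_a − p_p.
- Dropped patients as non-responders: difference = p_a(1 − w_a) − p_p(1 − w_p).
- Gap = p_a·w_a − p_p·w_p.

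**Assumed inputs.** 70 per arm, p_a = 0.40, p_p = 0.22, so the rule always reports 18.0 points. Neither the response rates nor the losses are in the SAP.

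| Early loss, active/placebo | Counted as non-responders | Points | 18.0 is larger by |
|---|---|---|---|
| 3% / 1% | 0.388 − 0.2178 | 17.0 | 6% |
| 5% / 1% | 0.380 − 0.2178 | 16.2 | 11% |
| 10% / 1% | 0.360 − 0.2178 | 14.2 | 27% |
| 15% / 3% | 0.340 − 0.2134 | 12.7 | 42% |
| 5% / 5% | 0.380 − 0.2090 | 17.1 | 5% |
| 5% / 9% | 0.380 − 0.2002 | 18.0 | 0% |

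Unstratified pooled two-proportion p-values, first with dropped patients as non-responders and then under the 7-day rule, are 0.028 and 0.023 for 3%/1%, and 0.063 and 0.025 for 10%/1%.

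**Direction.** The gap is zero when w_p/w_a = p_a/p_p, here 0.40/0.22 = 1.82. Equal losses still stretch a real difference by 1/(1 − w), but they create none where there is none. Whole-patient examples, also assumed:

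- 21 vs 21 responders of 70, 7 and 2 dropped: 0.0 becomes 33.3% − 30.9%, or 2.5 points before rounding.
- 21 vs 21, 7 and 7 dropped: 0.0 stays 0.0.
- 28 vs 14, 2 and 7 dropped: 20.0 falls to 41.2% − 22.2% = 19.0 points.

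**The case against.** The strongest reply is that no confirmatory result depends on these analyses. They are labelled sensitivity analyses and lie outside the hierarchy in SAP Table 3. Tests 2 and 4 use the whole treatment period with no 7-day rule, and Table 9.1.1 will show that result beside the period results in Table 9.1.3. This stands.

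A reader might infer that the maintenance-period differences are inflated. The documents do not support that as a fact. Addendum 2.3.3 covers the whole treatment period and gives neither counts nor timing, while the bias needs an imbalance before the cut-off day. Greater early loss on placebo could cancel or reverse it. The addendum is also post hoc, so the imbalance is no evidence of intent when the rule was set.

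A reader might also infer that everyone who withdrew leaves the maintenance analysis. That is too broad. A patient with 7 maintenance days who withdraws later stays in and, if the parent rule carries over, counts as a non-responder. SAP 5.1.1.1 uses data collected after withdrawal for the primary variable. If that carries over here, some early withdrawers would stay in too.

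Finally, the parent clause could be read as restricting the denominator to patients who did not withdraw, and the contrast would then disappear. The ITT label and the open-label sentence favour the non-responder reading. The completers-only reading would extend the selection to the main test, so it is another reason to state the rule outright.

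**Conclusion.** The inconsistency is real. Analyses presented as ITT repeats of the parent treat early withdrawers differently from the parent, and withdrawal was higher on each active arm. The period-specific responder and seizure-freedom differences can therefore be biased towards active.

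The size cannot be computed from the SAP. For the whole maintenance period, where only data ending before about Day 35 trigger the exclusion, a modest effect is plausible: 1.0 point on 18.0 at 3%/1% loss. Later 4-week blocks can accumulate more loss: 10%/1% gives 3.8 points. The 15%/3% row marks the upper end of the range tried and has no support in the documents as a figure for the whole maintenance period. All of this rests on the assumed response rates and losses, on the non-responder reading of the parent clause, and on withdrawn patients having no further data. The point concerns how supportive results are read. It does not touch the trial's confirmatory conclusions.

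**What to change.** In SAP 5.5.3.1.1 and 5.5.3.2.1, state for the responder and seizure-freedom analyses by period:

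- Every ITT patient who withdrew during the treatment period stays in the denominator as a non-responder, as in the parent analysis, whatever the number of days of data in that period.
- The 7-day minimum excludes only patients who did not withdraw but have fewer than 7 reported days in the period. Their number is reported by arm.

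Tying the rule to withdrawal at any time in the treatment period matters. A rule limited to withdrawal before or during the period would let a patient who left in Week 15 count as a titration responder, which the parent analysis does not allow.

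The current 7-day version may stay as a labelled supplement. The negative binomial rate analyses keep their 7-day rule.

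The cost is a few sentences and a denominator change in Table 9.1.3 and in the period tables that borrow the 5.5.3.2.1 methods (total seizures and individual seizure types). Period-specific responder percentages become slightly less favourable. Since the addendum already describes withdrawal by arm, a change made now should be documented as made with that knowledge.

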3. INVESTIGATIONAL PLAN

3.1 Trial Design

This multicenter trial consists of a randomized, placebo-controlled, double-blind phase followed by an open-label extension (OLE) phase.

Blinded Phase:

The blinded phase of the trial is a randomized, double-blind, parallel-group, 16-week comparison of two doses of GWP42003-P vs. placebo. Patients will complete a 1-week screening period and a 4-week baseline period before they are randomized to receive either 25 mg/kg/day GWP42003-P, 50 mg/kg/day GWP42003 P or placebo. Randomization will be stratified by age according to the following ranges: 1–6, 7–11, 12–17 years and 18–65 years. Patients will begin a 4-week dose escalation period, titrating up to their assigned dose, before continuing on a stable dose of blinded Investigational Medicinal Product (IMP) for 12 weeks.

Dose escalation for each patient is subject to the investigator's assessment of safety and tolerability. If a dose becomes poorly tolerated, the investigator may consider temporarily or permanently reducing the dose for the remainder of the trial.

Following completion of the blinded phase, patients will be invited to continue to receive GWP42003-P in an OLE.

Those patients opting not to enter the OLE will complete a 10-day taper period (down-titrating 10% per day for 10 days).

Open-label Extension Transition:

In order to maintain consistent exposure to IMP and maintain the integrity of the blind, patients will enter a 2-week blinded transition to the OLE. OLE IMP will be titrated up to 25 mg/kg/day whilst blinded IMP is simultaneously tapered down to zero. All patients will complete the transition and enter the OLE taking 25 mg/kg/day GWP42003-P:

- Patients from the placebo arm will titrate up to 25 mg/kg/day GWP42003-P.
- Patients from the 25 mg/kg/day GWP42003-P arm will continue to take 25 mg/kg/day GWP42003-P.
- Patients from the 50 mg/kg/day GWP42003-P arm will taper down (10% per day) to 25 mg/kg/day GWP42003-P.

Open-label Extension:

The OLE consists of a 3-week titration period followed by a maintenance period and a 10-day taper period. The initial OLE period will last for a maximum of 1 year.

Following titration according to the titration schedule, patients will continue with their optimal GWP42003-P dose. However, investigators may decrease the dose if a patient experiences intolerance, or increase the dose to a maximum of 50 mg/kg/day if required for better seizure control, until the optimal dose is found.

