5.5 Efficacy Analysis

5.5.1 General Approach

Blinded Phase:

The primary analyses will use the ITT analysis set. Further analyses using the PP analysis set will also be performed for the primary endpoint and secondary endpoints where specified in the sections below.

The primary null hypothesis is:

- Following 16 weeks of treatment there is no difference in effect between the 25 mg/kg/day GWP42003-P treatment arm and the placebo treatment arm in terms of the change in number of TSC-associated seizures during the treatment period compared to baseline.

The null hypothesis will be rejected if there is statistical evidence of a difference between the treatment arms at the α -level of 0.05 for the primary endpoint.

Statistical hypothesis testing will be performed on the primary endpoint and other endpoints as appropriate. Each endpoint, including the primary will have 2 comparisons against placebo (25 mg/kg/day GWP42003-P vs. placebo and 50 mg/kg/day GWP42003-P vs. placebo). Also, 3 key secondary endpoints have been defined.

The primary and key secondary endpoints will be tested with their Type I error controlled by use of a hierarchical gate-keeping procedure, in the sequence given in Table 3. One must reject the null hypothesis of an endpoint at the level of 0.05 (2-sided) to test the hypothesis of the subsequent endpoint in the sequence at the level of 0.05 (2-sided). If a null hypothesis is not rejected then testing will stop and all subsequent analyses will be declared not statistically significant.

Table 3 Hierarchy for Analysis

Test	Endpoint	Treatment Comparison
1	Primary endpoint	25 mg/kg/day GWP42003-P vs. Placebo
2	1 st key secondary endpoint	25 mg/kg/day GWP42003-P vs. Placebo
3	Primary endpoint	50 mg/kg/day GWP42003-P vs. Placebo
4	1 st key secondary endpoint	50 mg/kg/day GWP42003-P vs. Placebo
5	2 nd key secondary endpoint	25 mg/kg/day GWP42003-P vs. Placebo

6	3 rd key secondary endpoint	25 mg/kg/day GWP42003-P vs. Placebo
7	2 nd key secondary endpoint	50 mg/kg/day GWP42003-P vs. Placebo
8	3 rd key secondary endpoint	50 mg/kg/day GWP42003-P vs. Placebo

All statistical tests will be 2-sided and use the 5% significance level.

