5.5.2 Primary Efficacy Endpoint

Blinded Phase:

The primary endpoint is the change in number of TSC-associated seizures (see Section 5.1.3.7) during the treatment period (see Section 5.1.3.4) compared to baseline period (see Section 5.1.3.1) in patients taking GWP42003-P compared with placebo.

The primary endpoint will be analyzed using a negative binomial regression model with the total number of TSC-associated seizures during the baseline period and treatment period as the response variables.

A mixed effect model with repeated measures will be performed modelling the observed total number of TSC-associated seizures in the baseline period and treatment period implemented within the framework of general linear models using the negative binomial response distribution. The model will include stratified age group (1–6 years, 7–11 years, 12–17 years and 18–65 years), time, treatment arm and treatment arm by time interaction as fixed effects and patient as a random effect. The log transformed number of days in which seizure data were reported will be included as an offset. The time variable corresponds to an indicator for the baseline period and treatment period.

The GLIMMIX procedure in SAS will be utilized to perform the analysis with the option `maxopt=300` applied. If the model fails to converge, then the statement `'nloptions tech=nr ridge;'` will be added. If convergence is still not achieved, then `'method=laplace'` will be utilized. However, if convergence is still not possible, then the model will be changed to utilize the log normal response distribution (log rate model). If the log rate model is required and there are patients with no seizures during the baseline or treatment period then all patients will have their baseline and treatment period seizure count adjusted by adding a value of 1.

The estimated least squares mean seizure rate for each period and the estimated ratio of least squares means for treatment period to baseline period and 95% confidence intervals (CIs) will be presented for each treatment arm. In addition, the estimated ratio of each GWP42003-P arm to placebo and 95% CIs will be presented along with the p-value testing the null hypothesis that this ratio is 1.

For each ratio and upper and lower bound of the 95% CI, the percentage reduction will also be presented, calculated as:

$$[1 - (X \div Y)] \times 100\%$$

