5.5.4.5 Subject/Caregiver Global Impression of Change in Seizure Duration

Blinded Phase:

The SGICSD and CGICSD comprise the following questions to be rated on a 3-point scale for each seizure type:

CGICSD:

- Since the patient started treatment, please assess the average duration of the patient's seizures (comparing their condition now to their condition before treatment) using the scale below.

SGICSD:

- Since you started treatment, please assess the average duration of your seizures (comparing your condition now to your condition before treatment) using the scale below.

The 3 possible responses are:

- Decrease in average duration.
- No change in average duration.
- Increase in average duration.

The patient/caregiver will be asked to assess the average duration of seizures at Visit 3 (prior to commencement of IMP) as a memory aid for assessment further visits.

Each response will be coded with a score from 1 to 3, where 1 = Decrease in average duration, and 3 = Increase in average duration.

For each seizure type, the SGICSD and CGICSD will be summarized separately by treatment arm.

It is anticipated that only a small percentage of patients will complete the subject version of the questionnaire. Hence, no analyses will be performed for the SGICSD.

A combined score will be used as the primary analysis for this endpoint. The combined score will be defined as follows:

- If both a CGICSD and SGICSD are completed then the CGICSD will be used.
- If only a CGICSD is completed then the CGICSD will be used.
- If only a SGICSD is completed then the SGICSD will be used.

Proportional odd modelling will be carried out by including treatment arm and age group as factors. The estimated odds ratio (GWP42003-P vs. placebo), 95% CI for the odds ratio, and the p-value testing the null hypothesis that the odds ratio is equal to 1, will be presented.

Since this analysis uses a combination of caregiver and subject ratings, a sensitivity analysis will be performed using only the CGICSD score and using the same analyses as above.

Open-label Extension:

Descriptive summaries described above for the blinded phase will be repeated for OLE visits.

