Clinically Significant	21 to 24	
Elevated	18 to 20	
Average	1 to 17	

The v-scale score from the 11 adaptive behavior subdomains, 3 maladaptive behavior subdomains and the maladaptive behavior index, and the standard score from the 4 adaptive behavior domains and the adaptive behavior composite, recorded at each visit, will be summarized, on a continuous scale, by treatment arm. The change from baseline will also be included.

The change from baseline to the end of treatment visit, for the 4 adaptive behavior domains, the adaptive behavior composite and the maladaptive behavior index only, will be analyzed using the same ANCOVA approach as specified in Section 5.5.3.2.4.

The adaptive level from the 11 adaptive behavior subdomains, 4 adaptive behavior domains, the adaptive behavior composite, the 3 maladaptive behavior subdomains and the maladaptive behavior index, recorded at each visit, will be summarized, on a categorical scale, by treatment arm.

The adaptive level from the 4 adaptive behavior domains, the adaptive behavior composite and the maladaptive behavior index only will be analyzed using ordinal logistic regression. Factors for treatment and age group will be included along with the baseline adaptive level as a covariate. The estimated odds ratios (GWP42003-P arms vs. placebo), 95% CI for the odds ratios, and the p-values testing the null hypothesis that the odds ratio is equal to 1, will be presented.

Each adaptive level for adaptive behavior will be coded with a score from 1 to 5, where 1 = Low, and 5 = High. Each adaptive level for the maladaptive behavior index will be coded with a score from 1 to 3, where 1 = Clinically Significant, and 3 = Average.

The individual responses within each domain will not be listed, only the derived information for each subdomain and domain will be listed.

Open-label Extension:

Descriptive summaries described above for the blinded phase will be repeated for OLE visits.

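### The proportional-odds models for S/CGIC (Tests 5 and 7) and PGIC leave out the age group that stratifies randomization; the tests stay valid but lose power if age predicts the rating

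*SAP*

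**What the plan says.** SAP Section 3.1 sets the design: "Randomization will be stratified by age according to the following ranges: 1–6, 7–11, 12–17 years and 18–65 years".

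For S/CGIC, Section 5.5.3.1.2 specifies ordinal logistic regression of the 7-point score, with the last visit as the main analysis: "Proportional odds modelling will be carried out by including treatment arm as a factor". The CGIC-only sensitivity analysis uses the same model. Section 5.5.3.2.6 gives the identical specification for PGIC.

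Elsewhere the plan accounts for age group:

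- Primary endpoint (Section 5.5.2): "The model will include stratified age group (1–6 years, 7–11 years, 12–17 years and 18–65 years), time, treatment arm and treatment arm by time interaction". Total seizures, the third key secondary endpoint, follows this model.
- First key secondary endpoint (Section 5.5.3.1.1): "analyzed using a Cochran–Mantel–Haenszel (CMH) test stratified by age group".
- Impression of change in seizure duration (Section 5.5.4.5, exploratory): "Proportional odd modelling will be carried out by including treatment arm and age group as factors".
- Vineland-II adaptive level (Section 5.5.4.6, exploratory): "Factors for treatment and age group will be included along with the baseline adaptive level as a covariate".

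Table 3 in Section 5.5.1 places the "2 nd key secondary endpoint" at Tests 5 (25 mg/kg/day) and 7 (50 mg/kg/day), with this rule: "If a null hypothesis is not rejected then testing will stop and all subsequent analyses will be declared not statistically significant".

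**The concern.** Of the four endpoints in the hierarchy, S/CGIC alone ignores the stratification factor. Two exploratory endpoints analysed with the same type of model are adjusted, while the confirmatory one is not. The SAP gives no reason, and neither Section 5.1 nor Section 5.5.1 has a general rule that would add the factor.

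The odds ratio is non-collapsible. If age group predicts the rating, leaving it out moves the estimated odds ratio toward 1 relative to the age-conditional value. Stratified randomization also balances age across arms, and a model that ignores this overstates the variability of the treatment contrast. The result is a conservative test with less power.

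At stake are Tests 5 and 7 directly. A miss at Test 5 also closes Tests 6 to 8, which include total seizures at both doses. Tests 1 to 4 come earlier and are unaffected. PGIC is not in the hierarchy, so for it only precision and consistency are at stake.

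**Working it through.** **1. The plan's own power figure (Section 3.2).** Inputs: reductions of 15% and 50%, so a difference of 35 points; SD 60; 70 per arm; two-sided 5% Mann-Whitney-Wilcoxon test. With p = Φ(35/(60√2)) = 0.660, Noether's formula gives

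N = (1.960 + 1.282)² / [12 × 0.25 × (0.660 − 0.5)²] = 136.8, or 68.4 per arm.

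Power at 70 per arm is 90.6%, so the stated 90% reproduces. It concerns seizure frequency only; the SAP gives no power or effect size for S/CGIC or PGIC. Only the 70 per arm is carried forward.

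**2. Simulation of the ordinal analysis.** From the SAP: 7 categories, three arms of 70 (placebo pooled), four age strata balanced across arms, two-sided 5% test of one dose against placebo.

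Assumed, because the SAP is silent:
- placebo category probabilities 0.08/0.15/0.22/0.40/0.08/0.05/0.02;
- stratum shares 30/25/20/25%;
- evenly spaced age effects with SD 0 to 1.0 on the log-odds scale;
- a conditional odds ratio of 1.0, 2.0 or 2.5, the same for both doses;
- no missing ratings.

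Each setting had 3,000 replicates. Both models were fitted to each data set and judged by the Wald test. Power is shown as treatment-only → with age group.

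| Age-effect SD | Power, OR 2.0 | Power, OR 2.5 | Median estimate by treatment-only model (true 2.0 / 2.5) | Type I error |
|---|---|---|---|---|
| 0 | 63.3 → 63.7% | 84.6 → 85.0% | 2.02 / 2.51 | 4.8 → 5.1% |
| 0.25 | 62.1 → 63.2% | 84.2 → 84.8% | 1.99 / 2.50 | 4.9 → 5.2% |
| 0.5 | 58.5 → 62.8% | 83.3 → 86.1% | 1.95 / 2.45 | 4.2 → 5.2% |
| 0.75 | 56.9 → 64.8% | 79.0 → 84.9% | 1.90 / 2.29 | 3.6 → 5.9% |
| 1.0 | 48.7 → 61.4% | 75.1 → 84.8% | 1.79 / 2.17 | 2.7 → 5.2% |

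Monte Carlo error is about 0.4 points for type I error. With age group included, the median estimates are 2.01 to 2.05 and 2.53 to 2.58.

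**3. Cross-check.** A standard approximation for the shrinkage of the log odds ratio is 1/√(1 + 0.346·SD²). It gives 0.96, 0.92 and 0.86 at SD 0.5, 0.75 and 1.0. The simulated factors at OR 2.0 are ln 1.954/ln 2 = 0.97, ln 1.900/ln 2 = 0.93 and ln 1.794/ln 2 = 0.84, which agree.

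**4. What these SDs mean.** The simulated stratum scores −1.5, −0.5, 0.5, 1.5 have mean −0.1 under the assumed shares. Their variance is 0.3×1.4² + 0.25×0.4² + 0.2×0.6² + 0.25×1.6² = 1.34, so the SD is 1.158. Youngest and oldest strata therefore differ by 3/1.158 = 2.59 SDs. The odds ratio between them is exp(2.59·SD): 1.9, 3.7, 7.0 and 13.4 at SD 0.25, 0.5, 0.75 and 1.0.

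**The case against.** Nothing in the specified analysis is invalid. A reader might infer that the S/CGIC odds ratio is biased or that the error rate is compromised. The documents do not support that: the unadjusted odds ratio is a legitimate marginal quantity, a different estimand from the age-conditional one, and the test errs on the conservative side. No SAP rule requires the stratification factor in every model.

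The size of the loss is also uncertain. Each patient is rated against their own condition before treatment, with a memory aid from Visit 3. This makes a strong age effect less likely, though it does not exclude one. The largest losses need a 13-fold difference in odds between the extreme age groups, and nothing in the SAP suggests that. Shrinkage of the odds ratio also overstates the gain, because adjustment raises the standard error slightly (0.3070 to 0.3094 at OR 2.0, SD 0.5).

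Nor is age adjustment universal elsewhere: the Wilcoxon test (5.5.2.1), the log-rank tests (5.5.4.10) and the Cochran-Armitage trend test (5.5.3.1.2, 5.5.3.2.6) are unadjusted. These are sensitivity or exploratory analyses.

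Finally, adding age has a side effect. With 7 categories, the overall score test for proportional odds has 5 degrees of freedom per model parameter. It would go from 5 × 2 = 10 to 5 × 5 = 25, so age alone could trigger the Cochran-Armitage analysis.

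All of this stands. It limits the gain and adds a detail to the fix, but it does not explain why the one unadjusted endpoint in the hierarchy should stay so.

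**Conclusion.** The omission is certain; the size of its consequence is not. The treatment-only models are valid, and the issue is efficiency and consistency with the rest of the plan. Under the assumptions above, the power lost for one dose against placebo is essentially nil if age is unrelated to the rating, about 1 point or less at SD 0.25, 3 to 4 points at 0.5, 6 to 8 at 0.75 and 10 to 13 at 1.0. With no age effect, adjustment cost no measurable power, so the trade-off favours including it.

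It would be tempting to read this as a material loss of power in a confirmatory test for both ratings. That goes too far: the SAP gives no age effect from which to claim a particular loss, and PGIC is not part of the confirmatory sequence. This is a free improvement, not a defect that undermines the analysis.

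**What to change.** In Section 5.5.3.1.2, for the combined score and the CGIC-only sensitivity analysis, and in Section 5.5.3.2.6, include treatment arm and stratified age group as factors, as Section 5.5.4.5 already does. Keep the treatment-only model as a sensitivity analysis.

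Base the proportional-odds check that triggers the Cochran-Armitage analysis on the treatment effect. One simple way is to take the 10-df score test from the retained treatment-only model.

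The cost is a phrase in two sections, a sentence on the check and one extra model fit per analysis. The age variable is already derived.

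This change belongs before unblinding. If the blind is already broken, leave the pre-specified test and the hierarchy as they are and report the age-adjusted model as a labelled supportive analysis. The SAP addendum describes its analyses as post hoc and compares withdrawals by treatment arm (Section 2.3.3), so this second route probably applies to the blinded phase.
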